#### **D. Safety Monitoring**

Obese recipients will be monitored for clinical safety by history (and standard exams when seen in person) by asking open ended and then directed questions. Subjects will be followed closely, as noted above. Follow up calls made by a study coordinator will be documented and follow up information is reviewed on the same day with a study physician if any symptoms of concern are identified. A physician plan for ongoing follow-up will be noted and implemented. In any case of adverse events identified as grade 2 (moderate severity) an in-person visit with an investigator, either in the GI or ID outpatient practices, will be encouraged.

An AE will be considered related if, in the judgment of the treating physician it is both temporally related to administration of the capsules, and there is no other reasonable alternative explanation, and the AE is not more reasonably attributed to progression of the underlying illnesses.

Any serious adverse event (SAE) assessed as possibly, probably, or definitively related to fecal transplantation will be reported in an expedited fashion to the IRB and FDA. SAE's are defined as any Grade 3 or 4 events as described on the attached AE grading chart, in addition to any event temporally associated with the study procedure that:

- results in death;
- is life threatening (places the subject at immediate risk of death from the event as it occurred);

- requires inpatient hospitalization or prolongation of existing hospitalization;
- results in a persistent or significant disability/incapacity;
- results in a congenital anomaly/birth defect;
- any other adverse event that, based upon appropriate medical judgment, may jeopardize the subject's health and may require medical or surgical intervention to prevent one of the outcomes listed above.

Investigator monitoring with IRB and FDA oversight/reporting is proposed.

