### Exclusion criteria

- Initiation or discontinuation of a medication known to affect body weight or insulin sensitivity within 3 months of enrollment (e.g. hormonal contraception, psychiatric medications: tricyclic antidepressants, monoamine oxidase inhibitors, paroxetine, escitalopram, lithium, olanzapine, clozapin, risperidone, carbamazepine, valproate, divalproex, mirtazapine)
- Use of weight-loss medications or diabetic medications in the preceding 1 year (e.g. metformin, sulfonyleureas, insulin, etc)
- Antibiotic use in the preceding 6 months
- Delayed gastric emptying syndrome
- Known chronic aspiration
- Swallowing dysfunction or oral-motor dyscoordination, or inability or unwillingness to swallow multiple large capsules
- Malabsorptive disorders including celiac disease, cystic fibrosis, irritable bowel syndrome, prior gastrectomy, bariatric surgery and any state of chronic diarrhea
- Pregnant women or women trying to conceive or women who are breastfeeding; women of child-bearing potential will have a urine or serum hCG test.
- Patients with an acute illness or an acute exacerbation of underlying co-morbid condition
- Subjects on high dose steroids ( $>40$  mg daily)
- Subjects on multiple/combination immunosuppressive regimens including high dose corticosteroids, calcineurin inhibitors, mTOR inhibitors, lymphocyte depleting biologic agents, anti-TNF agents.
- Patients with a history of HIV, hepatitis B, hepatitis C, decompensated cirrhosis, recent bone marrow transplant, other causes of severe immunodeficiency.
- Patients with a history of significant allergy to foods not excluded from the donor diet (excluded foods are tree nuts, peanuts, shellfish, eggs)
- Allergy to chocolate/cocoa or gelatin, or unwillingness to ingest gelatin (in placebo capsules).
- Screening labs: AST or ALT  $>3x$  normal; Hematocrit  $<33\%$ ; White Blood Cell count  $<3000$  cells/uL; ANC $<500$ ; Creatinine  $>2.0$  mg/dL
- Patients with abnormal bowel habits, e.g. constipation with  $<4$  bowel movements/week

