## **V. STUDY PROCEDURES**

Lean donors will undergo testing and follow procedures outlined in protocol 2014P002706. Main procedures will occur in the primary 12-week study period; a supplemental week 24 phone-call will be performed for a safety check. In addition, samples of the fecal collection will be stored at -80°C for further microbiome analysis.

Obese recipients will undergo the following procedures:

Phone Screen (10-20 minutes)

Screen Visit (30 minutes)

- Review eligibility and understand/see size of capsules
- Obtain informed consent
- Height, weight measurements to determine eligibility
- Screening labs: Complete blood cell count w/ differential, comprehensive metabolic panel, HIV Ab, HBV sAb/sAg, HCV Ab, fasting insulin and glucose.
- Subjects will be counseled not to start any new major dietary changes, exercise regimens, or medications throughout the primary 12-week study period
- Subjects will be given information about how to perform fecal collections (see Stool Collection document)

Baseline Visit, Week 0 (Day 1: 5 hours, Day 2: 15 minutes, Day 3: 15 minutes)

- Fasting blood samples for measurements of HOMA-IR, lipids, CRP, and HbA1c.
- Women of child bearing potential will have a urine pregnancy test
- Height, weight measurements
- 48-hour food recall
- Whole body DXA scan for body composition analysis
- DXA scan of lumbar spine and hip to assess baseline BMD (optional substudy)
- Fecal collection
- Indirect Calorimetry
- Hyperinsulinemic euglycemic clamp
- After above study procedures are complete, subjects will receive FMT (or placebo) caps, 15 capsules on each of 2 successive days. Note that participants will need to either fast for 4 hours after the clamp or return on the subsequent day for their first capsule administration.

Weeks 1-5 (15 minutes)

- Interval side effect assessment (see Side Effect Assessment document)
- Subjects return for weekly administration of 15 capsules (for a total of 6 weeks, including Week 0)
- Fecal collection at weeks 1, 3 and 5.

Week 6 (5 hours)

- Interval side effect assessment (see Side Effect Assessment document)
- Height, weight measurements
- Women of child bearing potential will have a urine pregnancy test

- Fasting blood samples for measurements of HOMA-IR, lipids, CRP, and HbA1c.
- 48-hour food recall
- Fecal collection
- Whole body DXA scan for body composition analysis
- Fecal collection
- Indirect Calorimetry
- Hyperinsulinemic euglycemic clamp

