#### Week 12 (1 hour)

- Interval side effect assessment (see Side Effect Assessment document)
- Height, weight measurements
- Fasting blood samples for measurements of HOMA-IR, lipids, CRP and HbA1c.
- 48-hour food recall
- Women of child bearing potential will have a urine pregnancy test
- Whole body DXA scan for body composition analysis
- Fecal Collection

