## **VI. BIostatistical Analysis**

Change in insulin sensitivity is the primary outcome and will be compared between placebo and FMT groups over 12 weeks using longitudinal regression models. Secondary outcomes including change in insulin sensitivity, lipids, CRP, and DXA body composition will be similarly investigated. This is a pilot study to determine feasibility

and safety, and to obtain data for power calculations for a larger powered study. After accounting for 15% dropout rate, and assuming a standard deviation of insulin sensitivity of 30-45% and a two-sided alpha of 0.05, this pilot study (n=12 per group) has 80% power to detect a 40-60% difference in insulin sensitivity between groups, and a 30-45% difference from baseline within each group. After accounting for 15% dropout rate, and assuming a standard deviation of weight loss of 5% and a two-sided alpha of 0.05, this pilot study (n=12 per group) has 80% power to detect a 6.6% difference in weight loss between groups, and a 5% difference in weight loss from baseline within each group.

Fecal samples from lean donors and obese recipients will be stored, as noted above. If funding allows in the future, these samples will undergo microbial analysis using 16S ribosomal DNA-based identification and deep sequencing techniques. Changes in the composition of the gut microbiota and metagenomic pathways will be correlated with clinical changes in metabolism.

Bone mineral density (BMD) of the spine, hip, and whole body will be assessed at baseline and at 12 months. This pilot study will provide preliminary data to explore the associations between BMD and gut microbiota prior to manipulation and after FMT.

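### Blood count and metabolic panel are scheduled only at screening, so no planned test after capsules start can show silent blood-count, liver or kidney change

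*Combined protocol and SAP*

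**What the plan says.** The Screen Visit list in section V includes "Screening labs: Complete blood cell count w/ differential, comprehensive metabolic panel", with viral serology and fasting insulin and glucose. The results serve eligibility: the exclusion criteria have an item beginning "Screening labs: AST or ALT" that sets limits on liver enzymes, hematocrit, white cells, neutrophils and creatinine.

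Neither panel appears at a later visit. The baseline and week 6 lists give "Fasting blood samples for measurements of HOMA-IR, lipids, CRP, and HbA1c", and week 12 gives "Fasting blood samples for measurements of HOMA-IR, lipids, CRP and HbA1c". Week 24 (in-person extension visit) and month 12 list the same four measurements. Weeks 1 to 5 list "Interval side effect assessment (see Side Effect Assessment document" and stool collection at some visits, with no blood draw.

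Section D describes safety monitoring of recipients as "monitored for clinical safety by history (and standard exams when seen in person", using open-ended and then directed questions. It also states "SAE's are defined as any Grade 3 or 4 events as described on the attached AE grading chart". That chart and the side-effect form are attachments outside the public text.

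Section VI says "This is a pilot study to determine feasibility", and the sentence goes on to name safety and data for a later power calculation. Aim 2 makes FMT-related adverse events a secondary outcome.

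**The concern.** A pilot that names safety among its purposes measures blood count, liver enzymes and creatinine once, before exposure, and never again on schedule. The fasting draws at weeks 6 and 12 already exist and a randomised placebo group is in place, so the usual obstacles to laboratory safety data (extra visits, extra needles, no control) do not apply.

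At stake is one component of the safety result. A rise in liver enzymes or a fall in white cells without symptoms would not reach the adverse-event listing, and the report could say nothing about it by arm. Entry is also allowed with liver enzymes up to three times normal, so a participant may start with raised values and have no planned recheck. Finally, Grade 3 and 4 events count as serious, and section E ties a safety pause to related serious events. If the attached chart grades blood-count, liver or kidney values, those grades have no scheduled source of data.

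**Working it through.** **Step 1. Schedule.** Each visit list in section V was read for the relevant tests.

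| Visit | Blood count and metabolic panel | Fasting HOMA-IR, CRP, lipids, HbA1c |
|---|---|---|
| Screening | Yes | Fasting insulin and glucose only |
| Week 0 | No | Yes |
| Weeks 1–5 | No | No blood draw listed |
| Week 6 | No | Yes (plus clamp glucose and insulin) |
| Week 12 | No | Yes |
| Week 24, extension only | No | Yes |
| Month 12, extension only | No | Yes |

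The two panels appear at one visit before capsules and at none afterwards. The main study has two fasting draws after dosing starts.

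**Step 2. The plan's own figures.** The plan gives no figure for laboratory safety. Its power statement fixes the number of completers: 12 × 0.85 = 10.2, so about 10 per arm. With 10 per arm, 80% power and two-sided alpha 0.05, the t-test detectable difference is 1.325 SD between groups and 0.996 SD within a group.

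- Between groups: 1.325 × 30% = 39.7%, 1.325 × 45% = 59.6% (stated 40–60%); weight 1.325 × 5% = 6.62% (stated 6.6%).
- Within group: 0.996 × 30% = 29.9%, 0.996 × 45% = 44.8% (stated 30–45%); weight 0.996 × 5% = 4.98% (stated 5%).

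The stated figures reproduce, so 10 per arm is the right number to carry forward. Nothing in this point changes them.

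**Step 3. Size of the addition.**

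- No dropout: 24 participants × 2 draws = 48 panels.
- Planned dropout: 10 per arm × 2 arms × 2 draws = 40 panels, of which 10 × 2 = 20 are in FMT recipients.

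The two readings on one person are correlated, so the participant is the unit in the next step.

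**Step 4. What 10 to 12 FMT recipients could show.** The documents give no rate for a new abnormality, so a range is assumed. The probability of at least one affected recipient is 1 − (1 − p)^n.

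| Assumed true rate p | n = 12 | n = 10 |
|---|---|---|
| 5% | 1 − 0.95^12 = 46% | 1 − 0.95^10 = 40% |
| 10% | 1 − 0.90^12 = 72% | 1 − 0.90^10 = 65% |
| 20% | 1 − 0.80^12 = 93% | 1 − 0.80^10 = 89% |

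Under the present schedule no planned test would show a silent case, whatever the rate.

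If no recipient is affected, the one-sided 95% upper bound on the true rate is 1 − 0.05^(1/n): 22% for n = 12 and 26% for n = 10.

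**The case against.** The strongest reply is that the plan neither contradicts itself nor miscalculates here, and that the documents give no reason to expect this kind of toxicity. The background section's remarks on hepatic fat storage and absorbed bacterial fragments describe postulated roles of gut microbiota, not harms of donor capsules. The risk section lists infection, acquired illness, gastrointestinal symptoms, fever and bezoar, but no blood-count, liver or kidney effect. All of this stands: the point is a gap in measurement, not a predicted harm.

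A reader might infer that the trial cannot detect any laboratory harm, or that it rests on symptoms alone. The documents do not support either reading. CRP, lipids, HbA1c and HOMA-IR are measured at baseline, week 6 and week 12, so inflammatory, lipid or glycemic worsening can be compared by arm. Section D includes standard exams at in-person visits and same-day physician review when a follow-up call finds symptoms of concern, and nothing prevents tests prompted by symptoms.

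Exposure is also easily overstated. The schedule gives 15 × 2 + 15 × 5 = 105 capsules, but that is the scheduled maximum, and they contain donor material only in the FMT arm. Nor are the screening values wasted: they decide eligibility. Their interval to the first capsule is not stated, which makes them an imperfect baseline.

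The attachments may deal with laboratory values. The visit lists make a hidden schedule of panels unlikely, but the public text cannot exclude it.

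Finally, repeat panels in so few people can exclude little. That is true and limits what the fix can claim, but a small sample is not a reason to leave an existing draw untested when frequent changes would probably be seen.

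**Conclusion.** The concern holds in a limited form. As scheduled, 0 of 24 participants has a planned blood count or metabolic panel after the first capsule, so silent blood-count, liver or kidney change can be neither shown nor compared between arms in a pilot that has safety as a purpose. This is an inexpensive improvement to the assessment schedule, not an error in the analysis.

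A reader might also infer that adding the panels would let the pilot establish laboratory safety. It would not: zero events in 10 to 12 FMT recipients is compatible with a true rate of up to about 22% to 26%.

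The conclusion assumes that the visit lists are complete and that the unseen attachments schedule no further blood tests. The detection probabilities rest on assumed rates of 5% to 20%, on independence between participants, and on the abnormality being present at a draw; a change that resolved before week 6 would still be missed.

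**What to change.** Add the screening complete blood count and comprehensive metabolic panel to the existing week 6 and week 12 fasting draws. In section VI, state that change from screening will be summarised descriptively by randomised arm, with no hypothesis test. Grade any abnormality with the protocol's own adverse-event chart, if it covers laboratory values. The screening limits are entry criteria, and nothing in the documents establishes them as thresholds for harm, so they should not be used for this without justification.

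State the limit alongside the result: with 10 to 12 FMT recipients, zero events leaves a one-sided 95% upper bound of about 22% to 26%.

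Update the blood-volume figures in section VII, now about 200 ml over 12 weeks and 260 ml over 12 months with the extension.

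Cost: a short amendment, at most 48 routine panels (about 40 with the planned dropout), and a few more ml per draw. The last is an assumption, since the documents give no tube volumes. No visit or venipuncture is added, and dosing, stopping rules and sample size are unchanged.

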### Contributions of this study to the field

We believe that transfer of the “lean” microbiota to an obese recipient may lead to weight loss and metabolic improvements. Therefore, we propose to conduct a randomized double-blind placebo-controlled pilot study to evaluate the safety and effectiveness of oral FMT administration on weight and metabolism in obese adults. This highly innovative study will leverage this new non-invasive FMT technique to promote durable changes in the gut microbiome, and could represent a new horizon of treatments for

obesity and insulin resistance. Future studies including microbiomic analysis may identify specific strains of beneficial organisms to help narrow treatments from generic FMT to specific probiotic strains. Identification of specific microbes and metagenomic pathways will also aid in our understanding of the mechanism by which the gut microbiome controls response metabolism.

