## II. SPECIFIC AIMS

We propose a randomized placebo-controlled trial to study the impact of gut microbiome alterations on weight, insulin sensitivity, and other important metabolic endpoints.

**Aim 1.** To identify and characterize healthy lean donors from a phenotypic perspective to generate FMT capsules for a clinical trial in obese subjects.

**Aim 2.** To determine the impact of oral capsulized FMT from healthy lean donors on insulin sensitivity in obese adults in a 3-month randomized double-blind placebo-controlled trial. Secondary outcomes include changes in body weight, metabolic markers, and FMT-related adverse events. We hypothesize that FMT recipients will experience an improvement in insulin sensitivity and other metabolic endpoints. An optional extension study will evaluate the durability of gut microbiome change at 12 months.

**Aim 3.** To explore associations between the gut microbiome and bone density.

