FMT and placebo capsule administration: Subjects will be NPO at least 4 h prior to and for 1 hour following capsule intake on each day, to minimize risk of vomiting during ingestion of capsules. Subjects will be handed each capsule by an investigator and asked to take each capsule with a sip of water. Subjects will be asked to drink at least 12 oz of water during administration to facilitate dilution of stomach contents and transit into the small intestine. In the event of vomiting subjects will be observed, and not re-dosed.

Subjects are evaluated after taking capsules by the study investigators, typically for 15 minutes. Immediate side effects are very uncommon in our experience. Capsules are odorless and tasteless and do not dissolve in the acidic environment of the stomach. (In our study of capsules to date we have had 1/61 subjects who complained of nausea during administration, and this individual had concurrent psychiatric illness and concurrent irritable bowel syndrome diagnosed by an outside gastroenterologist. One child vomited 4 hours after capsules were administered.).

Subjects receive a copy of the signed consent form to take home and an information sheet (attached) on symptoms to monitor and study physician phone numbers. All patients have our contact numbers and will be encouraged to call for any concerns. Subjects are asked to inform us if they require the initiation of antibiotics for intercurrent clinical illness, during the study period.

Subjects will receive capsules at weekly intervals ( $\pm$  2 days) for weeks 0-5.

Subject counseling: Subjects will be counseled to remain on the same diet that they are currently on and not to initiate any major exercise regimens throughout the primary 12 week study period. In addition, women with child-bearing potential will be informed that they need to use contraception throughout the study. If they are taking a hormonal contraceptive, they need to remain on such until the end of the study. If they are not using a hormonal contraceptive, they will need to use other forms of birth control, such as barrier methods with a spermicide, IUD, or abstinence. We will ask that they not actively initiate or discontinue hormonal treatments during the study, as this may confound our assessments of body weight and insulin sensitivity.

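### The only named safety outcome is limited to FMT-related adverse events, and no comparison of all adverse events by randomised arm is described

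*Combined protocol and SAP*

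**What the plan says.** Section I (Contributions of this study to the field) describes a "pilot study to evaluate the safety and effectiveness of oral FMT administration on weight and metabolism in obese adults". Section VI repeats the purpose: the pilot is meant to establish feasibility "and safety, and to obtain data for power calculations for a larger powered study".

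Aim 2 in section II names the outcomes: "Secondary outcomes include changes in body weight, metabolic markers, and FMT-related adverse events". It does not say what makes an event FMT-related.

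Section V.D (Safety Monitoring) has the only definition of a related adverse event in the text. In the treating physician's judgment, "it is both temporally related to administration of the capsules, and there is no other reasonable alternative explanation", and the event must not be better attributed to progression of underlying illness. The same section says that recipients are monitored "by asking open ended and then directed questions", which does not restrict collection by cause.

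Section VI says: "Secondary outcomes including change in insulin sensitivity, lipids, CRP, and DXA body composition will be similarly investigated". Adverse events are not in that list, and no tabulation of events by arm is described there or in sections V.D to V.F.

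Under Randomization in section IV, physician and subject are both blinded to the capsules.

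**The concern.** The harms foreseen in section VII are nausea, vomiting, diarrhea and fever. These are nonspecific. In one patient on one day there is often some other reasonable cause, and under the section V.D rule that is enough to make the event unrelated, even if the capsules caused it.

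A randomised, blinded, placebo-controlled trial does not need case-by-case attribution to estimate harm. Background events occur in both arms, and the difference in all events between the arms estimates what the FMT capsules add. An outcome that first removes every event with a competing explanation gives up part of that advantage. At stake is the safety estimate that this pilot hands to the larger study. Efficacy, dosing and the stopping rules are not affected.

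**Working it through.** **The plan's own figures.** The plan states no safety figure. Its efficacy figures reproduce: 12 × 0.85 = 10.2, taken as 10 per arm. With the t distribution, 80% power is reached between groups at 1.325 SD, which is 39.7% and 59.6% for SDs of 30% and 45%, and 6.62% for an SD of 5% (stated: 40-60% and 6.6%). They have no bearing on this point.

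**Can a capsule-caused event fail the rule?** The plan supplies some competing explanations itself.
- At baseline the insulin clamp comes on the day of the first capsules or the day before: "participants will need to either fast for 4 hours after the clamp or return on the subsequent day for their first capsule administration".
- Section V.C asks subjects to report "initiation of antibiotics for intercurrent clinical illness, during the study period", so other illness is expected to occur.
- Against this, the exclusion criteria remove many gastrointestinal conditions and acute illness at entry. Fewer explanations remain, but not none.

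**Data available.** Side effects are assessed at weeks 1, 2, 3, 4, 5, 6, 12 and 24, which is 8 per participant, or 8 × 24 = 192 without dropout. The optional extension adds more.

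**Effect of the filter.** Let b be the background rate, c the capsule-caused rate (placebo capsules assumed to cause none), and r and s the shares of background and capsule-caused events that pass the rule. Blinding makes r the same in both arms.

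Expected difference = (r·b + s·c) − r·b = s·c

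This is exact for event counts. With c = 4/12 (assumed):

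| s | Difference |
|---|---|
| 100% | 33 points |
| 75% | 25 points |
| 50% | 17 points |
| 25% | 8 points |

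For participants with any event it is only approximate, because one person can have both kinds. If the two kinds are independent, the difference is s·c·(1 − r·b). Take 6/12 v 2/12 for all events, so b = 2/12 and c = 1 − (6/12)/(10/12) = 0.40.
- s = r = 0.5: 0.5 × 0.40 × (1 − 1/12) = 0.18, below 0.33.
- s = 0.5, r = 0: 0.5 × 0.40 = 0.20, below 0.33.
- s = 1, r = 0: 0.40, above 0.33.

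So on this measure a filter that removes only background can enlarge the difference. One that also loses enough capsule-caused events shrinks it.

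**Precision at 12 per arm.** Exact unconditional 95% intervals (score statistic, two one-sided 2.5% tests inverted on a 0.01 grid), all counts assumed:

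| Case | FMT v placebo | Difference | 95% CI (points) |
|---|---|---|---|
| All events | 6/12 v 2/12 | 33 | −6 to 66 |
| Half of all events kept | 3/12 v 1/12 | 17 | −18 to 49 |
| Half of caused, no background kept | 2/12 v 0/12 | 17 | −11 to 48 |
| All caused, no background kept | 4/12 v 0/12 | 33 | 3 to 65 |

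The last row shows attribution helping, which is why it is worth keeping as a second column. The widths show that any such table is descriptive.

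**The case against.** The strongest reply is that the link is inferred. Aim 2 does not cite section V.D, and the definition stands among follow-up and reporting procedures, not in the analysis section. Aim 2 also introduces its outcomes as an open list. This stands: the text shows silence on an all-event table, and a reader who infers a decision to discard unrelated events goes beyond it. But if section V.D does not define the outcome, nothing shown does, and the same fix is needed. Section VI's list is also open, but read generously it brings in the Aim 2 outcome, which is still related events only.

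The Side Effect Assessment document and the AE grading chart are not in the text reviewed and may say how relatedness is judged. Section V.D also uses possibly, probably or definitively related for expedited reporting, which fits poorly with a strict yes/no rule. Both points stand as limits. The graded wording is stated for serious events only, so it does not widen the outcome for nausea or diarrhea.

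The illustration may be too high. Section VII calls the expected events rare, and section V.C reports nausea during administration in 1 of 61 earlier subjects, about 12 × 1/61 = 0.2 per arm. That figure covers immediate effects in other patients, but it is a fair warning that the absolute loss may be small.

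A reader might also infer that the rule favours FMT or weakens safety oversight. The documents support neither. Attribution is blinded, serious events judged even possibly related are expedited, and the pause rule has its own wording.

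**Conclusion.** The point holds conditionally. If the section V.D definition governs the Aim 2 outcome, some nonspecific capsule-caused events can be left out in both arms, and the reported FMT-placebo difference could be too small. It rests on that reading, on at least some capsule-caused events having another plausible cause, and on attachments not shown leaving the rule as it stands.

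The amount is unknown. The fall from 33 to 17 points illustrates assumed counts and is not an estimate for this trial. It would be tempting to conclude that the safety result will be biased. The documents do not support that: they do not give the share of capsule-caused events that would fail the rule, a filter that removes mainly background could sharpen the contrast, and an all-event table can still be made from the same data. What is established is narrower: the named outcome is filtered by attribution, and the unfiltered blinded comparison is not described. Minor severity, and a cheap improvement.

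**What to change.** In Aim 2 and section VI, define the safety outcome as all adverse events after first dose, by randomised arm, regardless of attribution. For each arm report the number of participants with:
- any adverse event;
- any gastrointestinal adverse event;
- any event of grade 2 or higher;
- any serious adverse event.

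Give the risk difference with an exact 95% confidence interval, labelled descriptive. Show the blinded physician's attribution as a secondary column.

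The cost is one phrase in Aim 2, two or three sentences in section VI and one short table, with no new data. The downside is that background events appear in both arms and can widen the interval: 3 to 65 points for 4/12 v 0/12, against −6 to 66 for 6/12 v 2/12.

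Side note: unless the attachments already do so, align the yes/no definition in section V.D with the graded wording used for expedited reporting (V.D) and the pause rule (V.E), so that a serious event with an alternative explanation can still be rated possibly related. If the attachments define these grades, a cross-reference is enough.
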